Management of Persistent Epistaxis Using Floseal Hemostatic Matrix

PROTOCOL IDENTIFYING NUMBER 001

PROTOCOL VERSION DATE June 8, 2015

GENERAL INFORMATION

Name and title of the investigators and sub-investigators responsible for the trial with address and phone numbers

[name] [name]

[name] [contact]

[name]

[name] [contact]

[name] BSc.

[name] [contact] [contact]

| Title | Management of Persistent Epistaxis using Floseal Hemostatic Matrix |
|--|---|
| Short Title | Floseal Epistaxis Study |
| Protocol Number | 001 |
| Phase | Phase 4 Clinical Trial |
| Methodology | Randomized open-label Trial |
| Study Duration | 1 Year |
| Study Center(s) | Single-Center, University of Alberta |
| Objectives | We wish to observe the effectiveness of Floseal Hemostatic Matrix in aborting persistent epistaxis with the end of bleeding being our primary outcome. We also wish to include measures of patient comfort and cost analysis of epistaxis treatment. |
| Number of Subjects | 60 |
| Diagnosis and Main Inclusion Criteria | Adult patients presenting for Otolaryngology Head and Neck Surgery consult in the Emergency Department with persistent epistaxis. |
| Study Product, Dose, | Floseal Hemostatic Matrix, 5mL |
| Duration of administration | 30 Minutes |
| Reference therapy | Standard nasal packing using gauze by a trained Otolaryngology resident |
| Statistical Methodology | This study is powered based on a non-inferiority analysis to compare the efficacy of Floseal at achieving hemostasis. We will perform standard chi-square statistical analysis to determine the significance of these outcomes. |

Study Summary

Table of Contents

| 1 | | BACKGROUND | .1 |
|----|-----|---|---------------------|
| | 1.1 | INVESTIGATIONAL AGENT | .1 |
| | 1.2 | PRECLINICAL DATA | .1 |
| | 1.3 | Risk/Benefits | .1 |
| | 1.4 | DOSE RATIONALE | .1 |
| | 1.5 | TRIAL CONDUCT | .1 |
| | 1.0 | POPULATION. | .2 |
| | 1./ | LII EKA I UKE | .2 |
| 2 | | TRIAL OBJECTIVES | .2 |
| 3 | | TRIAL DESIGN | .2 |
| | 3.1 | PRIMARY STUDY ENDPOINTS/SECONDARY ENDPOINTS | .2 |
| | 3.2 | Study Design/Type | .2 |
| | 3.3 | RANDOMIZATION | .3 |
| | 3.4 | TRIAL TREATMENT | .3 |
| | 3.5 | DURATION | .3 |
| | 3.6 | DISCONTINUATION | .4 |
| | 3.7 | DATA IDENTIFICATION | .4 |

1.1 Investigational Agent

Floseal Hemostatic Matrix. This agent is a health Canada approved treatment option that is already in use in a number of hospital settings. It is a hemostatic sealant composed of a human thrombin containing fraction and a collagen gel-like fraction. It is applied to the area of active bleeding to achieve rapid hemostasis.

1.2 Preclinical Data

Floseal has been previously shown to achieve hemostasis more effectively than traditional methods in a number of clinical settings. These include cardiac surgery, spinal surgery and topical bleeding. Gel like hemostatic agents have additional advantages such as ease of use, conformity to irregular surfaces and their bio absorbable properties eliminate the need for removal. A prospective clinical trial using 10 patients at the University of Alberta has already been conducted, however it was not a randomized clinical trial and did not look at outcomes in addition to hemostasis. We wish to expand upon this knowledge in the context of epistaxis in this study.

1.3 Risk/Benefits

Potential benefits to participating in this study include: A potentially faster and more effective way to achieve hemostasis and abort bleeding. An increased level of comfort and less pain compared to traditional nasal packing.

Potential risks to participating in this study include: A very small theoretical risk of transmission of human viruses due to the Floseal product containing human thrombin. This treatment is already a standard of care that is currently in use in the University of Alberta Hospital therefor the risks are no greater than what a patient might be exposed to already. Risks might also include discomfort from the placement of the packing or FloSeal in the nasal cavity.

1.4 Dose Rationale

Floseal Hemostatic Matrix comes in a standard size (5mL) and we will be using this dosing to achieve hemostasis.

1.5 Trial Conduct

This study will be conducted in compliance with the protocol approved by the University of Alberta Health Research Ethics Board (HREB), and according to Good Clinical Practice standards. No deviation from the protocol will be implemented without the prior review and approval of the HREB except where it may be necessary to eliminate an

immediate hazard to a research subject. In such case, the deviation will be reported to the HREB as soon as possible.

1.6 Population

Adult patients presenting to the Emergency Department at the University of Alberta who have persistent epistaxis and require OHNS consult.

1.7 Literature

- 2. Oz MC, Cosgrove DM 3rd, Badduke BR, et al. Controlled clinical trial of a novel hemostatic agent in cardiac surgery. *Ann Thorac Surg.* 2000;69:1376-1382.
- 4. Renkens KL Jr, Payner TD, Leipzig TJ, et al. A multicenter, prospective, randomized trial evaluating a new hemostatic agent for spinal surgery. *Spine*. 2001;26:1645-1650.

2 Trial Objectives

The objective of this study is to observe the effectiveness of Floseal Hemostatic Matrix as a treatment option for persistent epistaxis in patients requiring OHNS consult. We will determine effectiveness based on its ability to abort bleeding as well as outcomes of patient comfort and ease of treatment. Even if Floseal has equal effectiveness in treating nosebleeds as traditional packing, if it is much more comfortable for patients then it may be the favorable treatment.

3 Trial Design

3.1 Primary Study Endpoints/Secondary Endpoints

The primary endpoint of this study will be when hemostasis is achieved and there is no longer any active bleeding from the nasal cavity. Our secondary endpoint will be two days following the intervention when we obtain the telephone questionnaire results from the patients about pain level and comfort of the treatment.

3.2 Study Design/Type

This study will be a prospective randomized, open-label clinical trial.

- 1. Otolaryngology Service consulted for persistent epistaxis by Emergency department
- 2. Otolaryngology resident determines whether patient meets inclusion/exclusion criteria for the study
- 3. Informed Consent is obtained and participants are given a chance to ask questions
- 4. Participants will be randomized using a sealed envelope system to either experimental or control group
- 5. Group A receives traditional nasal packing

Group B receives treatment using FloSeal Hemostatic Matrix

- 6. Both Groups are followed to observe the primary endpoint of hemostasis (end of bleeding)
- 7. Hospital care or discharge continues as normal
- 8. Patients are telephoned or visited as inpatients 48 hours later to complete the comfort questionnaire

3.3 Randomization

This study will be randomized in an allocation concealment fashion with a randomized treatment group already established in an envelope in the treatment room prior to patients being enrolled in the study. The direct care team therefor has no control over the chosen treatment for the patients. Due to the nature of the treatment it is not possible to blind this study to either the direct care team or patient.

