4.4 Treatment of Subjects

The amount of time from patient admission to the emergency department until they are seen by an OHNS resident may be variable due to extraneous circumstances. Upon consult by OHNS if the patient meets the criteria for the study, informed consent will be obtained by a member of the research team (not the direct care team). They will have an opportunity to ask questions and sign the consent form.

a. Participants will be randomized using a sealed envelope system to either experimental or control group

b. Group A receives traditional nasal packing by a trained OHNS resident (merocel gauze)

Group B receives treatment using 5 mL of Floseal Hemostatic Matrix by a trained OHNS resident

c. Both Groups are followed to observe the primary endpoint of hemostasis (end of bleeding)

d. If hemostasis is not promptly achieved (as determined by the direct care team) than additional measures will be taken to arrest bleeding just as they would in any other non-study situation

e. Hospital care or discharge continues as normal

f. Patients are telephoned or visited as inpatients 48 hours later to complete the comfort questionnaire

We will have extra follow-up with these patients to observe the effects of our treatment on patient comfort and allow for the opportunity of a study debrief. This will occur two days following their treatment and should last no more than five minutes over the telephone.

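### Pre-filled envelopes kept in the treatment room before enrolment leave allocation concealment asserted but not assured

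*Protocol*

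**What the plan says.** Protocol section 3.3 states "This study will be randomized in an allocation concealment fashion" and describes the method as a "randomized treatment group already established in an envelope in the treatment room prior to patients being enrolled in the study". From this it concludes: "The direct care team therefor has no control over the chosen treatment for the patients". The same section says that neither the care team nor the patient can be blinded.

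Section 3.2 gives the order of events. The Emergency Department consults the service; then "Otolaryngology resident determines whether patient meets inclusion/exclusion criteria for the study"; then consent is obtained; then "Participants will be randomized using a sealed envelope system to either experimental or control group". Section 4.4 repeats the sealed envelope and the order, and adds that "informed consent will be obtained by a member of the research team (not the direct care team"). In both arms an OHNS resident gives the treatment (section 4.4). Under section 5.1 the resident providing direct care decides whether hemostasis is adequate.

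Neither document says whether the envelopes are opaque or numbered, who prepares, holds or opens them, whether openings are logged, or how the sequence is generated. The SAP does not mention randomization.

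**The concern.** Concealment means that whoever admits patients cannot learn the next assignment before committing to enrol. Section 3.3 argues for something narrower, namely that the care team does not choose the arm. A team that cannot choose the arm may still be able to choose who enters, if it can find out which arm comes next. Putting the prepared envelope in the treatment room ahead of enrolment gives access to the people from whom the assignment should be hidden.

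If the next assignment became known, a difficult bleed could be left out or deferred when one particular arm was due. The resulting imbalance arises before randomization, so the intention-to-treat analysis in section 7.2 does not protect against it, and two small arms leave little scope for adjustment. The bias could favour either arm.

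**Working it through.** **Does the text support the conclusion in section 3.3?**

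| Element | Text | Effect on concealment |
|---|---|---|
| Location and timing | In the treatment room before enrolment (3.3) | Weakens: access before the decision to enrol |
| Screening | Resident (3.2) | Weakens: screener belongs to the team expected to have access |
| Treatment and outcome | Resident, unblinded (4.4, 5.1, 3.3) | Gives an interest in who enters |
| Sealed envelope | 3.2 and 4.4 | Protects in part |
| Order: eligibility, consent, randomization | 3.2 and 4.4 | Protects in part; no rule that eligibility is recorded before opening |
| Consent by research team | 4.4 | Protects in part, but comes after the resident's screening |
| Opacity, numbering, custody, log | Not stated | Early opening, reading through or skipping is neither prevented nor detectable |

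That residents work in the treatment room follows from their giving the treatment; the protocol does not say so directly. On this comparison the claim of concealment is plausible but not secured.

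**Illustration of size.** The documents give no figure for this point, so what follows rests on assumptions.

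*Inputs from the SAP:* success 93% in each group, margin 25 points, α 5%, power 80%, 13 per arm. The SAP figure reproduces if α is one-sided:

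n = (1.645 + 0.842)² × 2 × 0.93 × 0.07 / 0.25² ≈ 12.9, so 13 per arm.

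*Assumed test:* a score (Farrington-Manning) test at one-sided 5%. Neither document names it. The protocol names chi-square and the SAP Fisher's exact test, and neither states a non-inferiority test.

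z = (p̂F − p̂C + 0.25) / √{[p̃F(1 − p̃F) + p̃C(1 − p̃C)] / n}, with p̃F and p̃C estimated under p̃F = p̃C − 0.25. Non-inferiority is declared if z > 1.645.

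*Cut-offs at 13 per arm.* If packing succeeds in 13/13, then p̃C = 1 and p̃F = 0.75, and the standard error is √(0.75 × 0.25 / 13) = 0.120.
- Floseal 13/13: z = 0.25 / 0.120 = 2.08, passes.
- Floseal 12/13: z = (0.25 − 0.077) / 0.120 = 1.44, fails.

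The minimum Floseal successes are 12, 12 and 13 when packing has 11, 12 and 13. One patient is 1/13 = 7.7 points.

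*False non-inferiority rate.* Sum the product of the two binomial probabilities over all passing results, with packing at 93% and true Floseal success at 93 − 25 = 68%. Steering is assumed to raise the observed Floseal success rate only.

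| Assumed gain from steering | Floseal success as enrolled | P(non-inferior) |
|---|---|---|
| 0 points | 68% | 4.0% |
| 5 points | 73% | 7.9% |
| 10 points | 78% | 14.5% |
| 15 points | 83% | 25.2% |

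*How much steering is that?* If a fraction f of the Floseal arm is replaced by easier bleeds whose success is higher by a gap g, the gain is f × g. With an assumed g of 30 points, gains of 5, 10 and 15 points need f = 0.05/0.30 = 17%, 33% and 50%, or about 2, 4 and 6 to 7 of 13 patients. The lower rows are therefore heavy steering.

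*Sensitivity to test and sample size.*
- With an unpooled Wald test at 13 per arm, Floseal 12/13 against packing 13/13 passes: (0.25 − 0.077) / √(0.923 × 0.077 / 13) = 2.34.
- With the protocol's 30 per arm and the same 25-point margin, the score test passes Floseal at 27/30 against 30/30: (0.25 − 0.10) / √(0.75 × 0.25 / 30) = 1.90. One patient is then 1/30 = 3.3 points.

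**The case against.** The strongest reply is that the protocol already contains the main protections. The envelopes are sealed, randomization follows eligibility and consent, and consent is taken by someone outside the care team. Preparing the assignment in advance is what concealment requires. The resident's discretion is also limited: the Emergency Department makes the consult before the resident screens, and the only listed exclusion, anticoagulants or other blood thinners, is a medication fact. All of this stands, and it lowers the risk.

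It does not remove the risk. Persistent epistaxis has no stated duration or severity threshold, the resident's judgement precedes consent, and no control on opening or skipping is described. The reply also does not explain why the envelope needs to be in the treatment room.

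A reader might go further and infer that the resident holds the envelopes, or that the next assignment will be known at screening. The documents support neither. They give a location but no custodian, and a sealed envelope reveals nothing unless it is opened early, can be read through, or the sequence is predictable. The text neither states nor excludes these.

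The unblinded judgement of hemostasis is a separate source of bias. It would remain wherever the envelopes were kept.

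**Conclusion.** The point holds as a weakness in a stated arrangement. Section 3.3 asserts concealment, but the location it gives, together with the absence of custody, opacity, numbering and logging, does not assure it. This is more than missing detail, because the protocol specifies a weaker arrangement when a better one is available within its own workflow. It does not show that allocation was or will be disclosed. The change should be made.

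The size is unknown. The rise from 4.0% to between 7.9% and 25.2% is illustrative only. It rests on the SAP's 13 per arm and 25-point margin, an assumed score test and assumed steering effects, and any other flaw that shifted Floseal success equally would give the same figures. A reader might infer that one steered patient reverses the trial's conclusion. That is possible only when the result lies at the cut-off, and the cut-off changes with the test and with the protocol's 30 per arm. The point does not depend on these figures.

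**What to change.** Change section 3.3, and align sections 3.2 and 4.4 with it, so that:
- envelopes are opaque, sequentially numbered and sealed, and are held outside the treatment room by the research-team member who takes consent;
- the next number is opened only after the resident has recorded eligibility and the consent form is signed;
- patient ID, date and time are written on the envelope at opening;
- every number, used or unused, is accounted for in the final report.

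The cost is a change of custody and a short log. A research-team member already takes consent, so no new role is needed. The drawback is that this member must be present, or reachable with the envelope, at randomization, which may be inconvenient for emergency consults.

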3.4 Trial Treatment

Patients in this trial will be receiving Floseal in the nasal cavity by a trained OHNS resident. The amount of Floseal required to stop bleeding and cover the wound site may vary. Floseal is packaged as a 5mL syringe set that requires set up before use. Detailed instructions on the use of Floseal sealant are provided in the Floseal safety monograph (attached in the ethics application) and residents will all have proper training.

3.5 Duration

The duration of treatment for patients in this study will be no longer than the standard practice treatment for their condition. Total time from admission to the Emergency Department and being seen by OHNS consult to achieve hemostasis using either Floseal or standard nasal packing may be variable, but should take no longer than a few hours. There will be an additional telephone survey completed at the patients discretion two days following their involvement in the study.

3.6 Discontinuation

Patients will be undergoing all aspects of the study under the supervision of a physician or research coordinator and will therefor be encouraged to express any concerns they have so they can be addressed as promptly as possible. We will minimize risk by providing the physicians involved with the most training possible to ensure placement of the treatment is done as easily and accurately as it can be. Patients who wish to withdraw from the study will be able to do so at any time and will be informed of this upon obtaining consent for the study.

As this is a minimal risk trial with a product that is already in the use in hospital settings it is very unlikely that we will need to discontinue the entire trial. In the unlikely event that this would occur, we would disclose the reasoning to the HREB and all other necessary regulatory agencies.

3.7 Data Identification

For this clinical trial we will need to have access to patient records to observe our primary endpoint of hemostasis as well as our secondary outcomes of patient comfort and a cost analysis. To obtain informed consent we will need the patients name and signature. For our statistical analysis we will need patient age and gender. To perform the patient comfort survey we will need the participant telephone number and email address.

Surname and First Name

Telephone Number

Email Address

Age at time of data collection

Health Care Number

Hospital Discharge Date

4 Selection and Withdrawal of Subjects

4.1 Inclusion Criteria

Adult patients with persistent epistaxis that present to the Emergency Department at the University of Alberta Hospital and require OHNS consult for their ongoing epistaxis.

4.2 Exclusion Criteria

For this trial we will exclude any patients taking anticoagulant medication or other blood thinners.

4.3 Subject Withdrawal

Patients will be undergoing all aspects of the study under the supervision of a physician or research coordinator and will therefor be encouraged to express any concerns they have so they can be addressed as promptly as possible. We will minimize risk by providing the physicians involved with the most training possible to ensure placement of the treatment is done as easily and accurately as it can be. Patients who wish to withdraw from the study will be able to do so at any time and will be informed of this upon obtaining consent for the study. They will be instructed to speak with any member of the direct care or research team to withdraw him or herself from the study. Patients will not be replaced as this study has a rolling enrollment and we will continue until we acquire the proper number of participants. Data from the withdrawn participants will be discarded, however we will keep the record of the patient themselves and follow-up with them as we would any other patient in the study (if they are willing) to monitor for any adverse events and ensure patient safety.

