5.1 Efficacy Parameters

Efficacy of the Floseal Hemostatic Matrix will be determined by observing whether patients receiving either the Floseal or control treatment require additional measures to abort bleeding. Our primary endpoint is hemostasis, however if hemostasis is not adequately achieved, as determined by the OHNS resident providing direct care, than additional measures will be taken to abort bleeding and this will signify our primary endpoint.

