7.2 Subject Population(s) for Analysis

We hope to have 60 patients total enrolled in this study (30 Floseal and 30 control). This sample size was chosen to provide the powering listed below. This level of significance is based on a non-inferiority trial. We chose this trial type because we seek to quantify the secondary benefits for this treatment, which is already in use. All randomized subjects will be included in the statistical analysis based on an intention-to-treat protocol.

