7.3 Significance

This is a non-inferiority trial with a power of 0.8, a non-inferiority limit of 5% and a significance level of P < 0.05.

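### Protocol 4.3 deletes the data of patients who withdraw while 7.2 promises intention-to-treat; at 13 per arm one deletion can reverse the non-inferiority verdict in either direction

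*Protocol*

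**What the plan says.** Protocol 7.2 defines the analysis population: "All randomized subjects will be included in the statistical analysis based on an intention-to-treat protocol".

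Protocol 4.3 gives a different rule for anyone who leaves: "Data from the withdrawn participants will be discarded". The only exceptions are the record of the patient and, if the patient is willing, follow-up for adverse events. Leaving is unrestricted in time: "Patients who wish to withdraw from the study will be able to do so at any time". The same section adds: "Patients will not be replaced as this study has a rolling enrollment and we will continue until we acquire the proper number of participants".

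Three other passages bear on when a withdrawal can occur.

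- Protocol 5.1 fixes the efficacy result at treatment. If hemostasis is inadequate, "additional measures will be taken to abort bleeding and this will signify our primary endpoint".
- Protocol 3.2 and 4.4 continue follow-up to a contact at 48 hours. Section 3.5 leaves that contact to the patient: "There will be an additional telephone survey completed at the patients discretion two days following their involvement in the study".
- Protocol 3.3 says that "it is not possible to blind this study to either the direct care team or patient".

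The SAP (Sample Size) plans 13 patients per arm with a 25% margin, 93% success in each group and 0% attrition. It names no analysis set and has no rule for withdrawals or missing outcomes.

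**The concern.** The two protocol rules are both current, and neither makes an exception for the other. When a randomized patient withdraws, the analyst has to break one of them, and could choose after seeing which choice helps.

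The word data in 4.3 is unqualified, so it covers the hemostasis outcome. That outcome exists within hours, while participation runs to 48 hours. A patient who knows the treatment and its result can withdraw, and a valid primary outcome then disappears. Declining the survey is not in itself withdrawal, so the concern is limited to actual withdrawals.

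Exclusions made after randomization can bias the comparison, and the documents do not tell us in which direction. Losing a Floseal failure favours non-inferiority; losing a packing failure works against it. Protocol 1.3 lists less pain than with packing as a potential benefit of Floseal, so equal withdrawal in the two arms cannot be taken for granted.

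The enrolment wording adds a second uncertainty: whether the target counts patients randomized or patients left for analysis. Topping up would restore the count but not the randomized comparison.

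**Working it through.** **The passages side by side.** Under 7.2 a randomized patient who withdraws is analysed; under 4.3 that patient's data no longer exist. The SAP's 0% attrition is a planning assumption and does not say what to do with a withdrawal. The contradiction therefore needs no calculation. The rest shows how much one deletion can matter.

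**Inputs from the SAP.** Success 0.93 in each arm, margin 0.25, alpha 0.05, power 0.80, 13 per arm.

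**The SAP's own figure.** n per arm = (z_alpha + z_beta)² × 2p(1 − p) / d² = (1.645 + 0.842)² × 2 × 0.93 × 0.07 / 0.25² = 12.88, so 13 per arm. This reproduces the SAP with a one-sided 5% level. One-sided 2.5% gives 16.35, so 17 per arm, which does not.

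**Assumed criterion.** Neither document names an interval or its sidedness. I took the lower score (Farrington-Manning) limit for Floseal minus packing: the value δ at which (p_F − p_P − δ) / √[q_F(1 − q_F)/n_F + q_P(1 − q_P)/n_P] equals 1.645 (or 1.960). Here q_F and q_P are the maximum-likelihood rates constrained to differ by δ. A trial passes if the limit lies above -25 points.

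**One deletion at 13 per arm** (Floseal v packing, limits in points):

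| Deleted patient | Before | After | One-sided 5% | One-sided 2.5% |
|---|---|---|---|---|
| Floseal failure | 11/13 v 12/13 | 11/12 v 12/13 | -31.4 fails → -23.8 passes | -36.3 → -29.3, both fail |
| Floseal failure | 12/13 v 13/13 | 12/12 v 13/13 | -28.2 fails → -18.4 passes | -33.3 fails → -24.2 passes |
| Packing failure | 12/13 v 12/13 | 12/13 v 12/12 | -21.9 passes → -28.2 fails | -27.2 → -33.3, both fail |

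If enrolment continues after the first deletion and adds a Floseal success, the table becomes 12/13 v 12/13, which passes at -21.9.

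**Does it depend on the interval?** The Wald limit is p_F − p_P − 1.645 × √[p_F(1 − p_F)/n_F + p_P(1 − p_P)/n_P].

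- 11/13 v 12/13: -0.0769 − 1.645 × 0.1244 = -28.2 points, fails. After deleting a Floseal failure, 11/12 v 12/13: -0.0064 − 1.645 × 0.1088 = -18.5, passes.
- 11/13 v 11/13: 0 − 1.645 × 0.1415 = -23.3, passes. After deleting a packing failure, 11/13 v 11/12: -0.0705 − 1.645 × 0.1280 = -28.1, fails.

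Reversals in both directions also exist under the Newcombe and Agresti-Caffo limits, and at both levels under all four methods, though not always for the same tables.

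**How many trials lie one deletion from a changed verdict.** Summing binomial probabilities over all 13 v 13 tables at 93% v 93%, with the score limit:

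| | One-sided 5% | One-sided 2.5% |
|---|---|---|
| Passes with everyone kept | 63.2% | 48.7% |
| Fails, but passes with one Floseal failure deleted | 24.6% | 32.3% |
| Passes, but fails with one packing failure deleted | 14.6% | 7.4% |

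The share that deleting any single patient could reverse, at one-sided 5%, is 16% (Wald), 25% (Agresti-Caffo) and 39% (Newcombe and score).

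**The protocol's own design.** Sections 7.2 and 7.3 give 30 per arm and "a non-inferiority limit of 5" per cent. At one-sided 5%, 29/30 v 28/30 (-7.9, fails) becomes 29/29 v 28/30 (-2.1, passes), but 28/30 v 28/30 fails before and after (-12.6, then -8.3). The two shares, at 93% v 93%, are 11.0% and 6.2%.

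**The case against.** The strongest reply is that the reversals rest on a criterion found in neither document. The protocol names a chi-square test and the SAP names Fisher's exact test. Fisher's p is 1.00 for every table of 12 or 13 per arm in the first table above, before and after deletion. That is correct, but Fisher's test of no difference does not assess a margin. A non-inferiority claim needs some comparison with the margin, and reversals occur under each of the four tried.

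The size does depend on the method. The score figures are at the top of the 16% to 39% range. The score limit also passes only 63.2% of trials against the SAP's planned 80%, so it was probably not the planning criterion. Under Wald, the 12/13 v 12/13 example does not reverse (-17.2, then -19.8); a different table does.

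Frequency may also be low. Treatment is short, the later contact is a call of about five minutes, only the patient can initiate a withdrawal under 4.3, and no rate is given. This stands: the risk is possible but not quantified. Unequal withdrawal is likewise plausible rather than shown, since 1.3 lists discomfort as a risk of either treatment.

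The enrolment sentence can be read coherently as no one-for-one replacement while rolling recruitment continues. What remains is whether the target counts patients randomized or analysed.

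Finally, a patient may withdraw consent for use of the data, so some outcomes could still be lost. The current text, however, deletes data for every withdrawal, whether or not the patient asks.

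**Conclusion.** The concern holds, and the text must be corrected before analysis. The contradiction between 4.3 and 7.2 rests on the wording alone and applies at either sample size. That one deletion can reverse the verdict in either direction at 13 per arm holds under all four interval methods and both levels tried.

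The 24.6% and 14.6% assume 93% success in both arms, a one-sided 5% score limit, the 25-point margin and exactly one deletion of the stated kind. They describe how close trials lie to a changed verdict, not how often it would change. The direction of any bias cannot be predicted from the documents.

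**What to change.** - In Protocol 4.3, replace the discard sentence: data collected up to withdrawal are kept and analysed in the allocated arm, using the observed hemostasis result, unless the patient withdraws consent for their use.
- Pre-specify one rule for a withdrawal before hemostasis is known, for example counting it as failure, with a sensitivity analysis under the opposite assumption.
- Define the target as patients randomized, and replace the sentence on replacement and continued enrolment with one that says so.
- Report withdrawals by arm.
- State the same analysis set in the SAP. A supportive analysis of patients treated as allocated is optional.

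The cost is one protocol paragraph and one SAP sentence, with no extra patients. The small drawback is that a few missing outcomes may be counted as failures; the sensitivity analysis would show the effect.
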